### **Outcomes of Clinical Assessment**

The following clinical assessments were performed throughout the study by the same examiner who was blinded to the treatment rendered to the subjects.

### **Clinical Periodontal Parameters**

When collecting data, the examiner was blinded to treatment groups. Using the same PVS (Exafast™ NDS, GC America, Alsip IL) impressions to fabricate stone models

(Microstone, Whipmix Corp., Louisville, KY) a customized stent was fabricated using a positive pressure thermoplastic mold device (Biostar® Scan/Biostar® V, Great Lakes Orthodontics, New York). This 1-mm thick, semi-rigid stent was used as reference for the linear measurements using a periodontal probe (15 UNC Color-Coded Probe, Hu-Friedy, Chicago IL). All the measurement will be at 1 mm increments. Clinical parameter measurements was taken at six sites (mesio-buccal, mid-buccal, disto-buccal, mesio-lingual, mid-lingual, and disto-lingual) of each tooth. Relative gingival recession (R-REC) was measured from a margin of the stent to the most coronal height of the gingival margin. PD was measured as the distance from the gingival margin to the depth of the pocket. The probe was held flat against the tooth near the gingival margin and inserted into the periodontal pocket in a path that is parallel to the long axis of the tooth and advanced using light pressure until slight resistance is felt. Relative attachment level (RAL) was measured from a margin of the stent to the bottom of the pocket.

Bleeding on probing (BOP) was measured with sites that show any bleeding within 30 seconds of probing and was recorded as a percentage.

Oral hygiene level was measured by using the Modified Quigley-Hein Plaque Index (MQH) with disclosing solution that measures plaque on all teeth except 3rd molars at 4 surfaces on the buccal and lingual surfaces where:

Score 0 has no plaque

Score 1 has separate flecks of plaque along the cervical margin of the tooth

Score 2 has a  $\leq 1$  mm band of plaque at the cervical margin of the tooth

Score 3 has a band of plaque  $> 1$  mm but  $< \frac{1}{3}$  of the crown of the tooth

Score 4 has plaque that is covering  $\geq \frac{1}{3}$  but  $< \frac{2}{3}$  of the crown of the tooth.

Score 5 has plaque covering  $\geq \frac{2}{3}$  of the crown of the tooth

Full mouth series of periapical and bitewing radiographs was captured for all patients for standard periodontal diagnostic procedure as a part of the comprehensive periodontal evaluation. Radiographs of patients that were referred other clinics taken within a year of the comprehensive periodontal evaluation was used.

### **Examiner Reproducibility**

Collection of clinical periodontal parameters was repeated in 6 patients for inter-examiner reproducibility. This was accomplished by randomly recalling some subjects for a second exam during the same session, as scheduling permits. Scoring at least one other subject before doing the repeat exam minimized the likelihood of the examiner recalling individual scores. Interclass/inter-examiner correlation (ICC) of overall variability was calculated and represented as an ICC score (SPSS, IBM Corporation, Armonk New York U.S.).

### **Randomization; Sequence, Allocation, and Implementation**

Subjects were assigned randomized identification (ID) numbers during enrollment (Visit 1), which will be recorded on all Case Report Forms (CRF) and the Product Accountability Log. Immediately following the preliminary clinical parameter recording the investigators randomly allocated subjects in a group using a predetermined random group assigner (SAS, SAS Institute, Cary NC) based upon subjects' ID numbers. Each subject received non-surgical periodontal therapy (SRP) as indicated in areas with increased probing depths.

## **Follow Up Care**

Patients enrolled in the study will be monitored for any changes in their periodontal status. If deterioration of periodontal conditions is noted (i.e. PD deepening and losing RAL >1.5mm with or without bleeding on probing), re-treatment of sites was recommended to the patient. Any sites requiring re-treatment, either non-surgical or surgical intervention will be excluded in final study data and will be treated as indicated.

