method combining mechanical and chemical debridement with 1.7% HP gel . The HP gel is directed into periodontal pockets via a custom tray, as an aid to manage biofilms better for patients with gingivitis and periodontitis. The FDA approved  $\leq 3\%$  HP gel as an oral debriding agent and an oral wound cleanser. The FDA also cleared the prescription tray branded as the Perio Tray® (Perio Protect, St. Louis, MO) as a subgingival delivery medical device in 2004 (21 C.F.R. § 872.6870). Customized extensions of the tray support the customized seal to direct the gel deep down into the sulcus or periodontal pocket and overcome the crevicular fluid flow .

Custom tray application of the HP gel as an adjunct to SRP in the treatment of chronic periodontitis has been investigated. In randomized controlled studies, it was demonstrated that significant reduction of probing depth (PD) and bleeding without mechanical intervention were seen after two weeks of HP prescription tray regimen followed by SRP and the results were maintained for up to six months with the daily use of HP prescription trays for 10 weeks . The prescription tray delivery of HP gel as an adjunctive to SRP was effective before and after full-mouth SRP in reducing PD about 1mm over SRP alone for six months in chronic periodontitis patients . However, there is currently no randomized control clinical study evaluating the differences in the duration effects of the treatment in chronic periodontitis patients with customized delivery of hydrogen peroxide gel.

The primary objectives of this randomized, controlled, single-blind, parallel clinical study are: (1) to examine if the prescription tray delivery of HP gel adjunctive to SRP results in a greater clinical improvement than SRP alone over a six-month period; and (2) to

evaluate whether the custom tray delivery of the HP gel can decrease inflammation prior to SRP.

The secondary objective is to compare if there is a difference between the length of treatment of adjunctive HP gel (3-months versus 6-months). It is hypothesized that adjunctive HP therapy will provide additional clinical benefits in PD reduction, attachment gain, and reduction of bleeding on probing (BOP) compared to SRP alone.

Null Hypotheses:

There is no significant difference between the treatment groups (SRP + HP13 vs. SRP + HP26 vs. SRP alone) with regards to reduction in PD.

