## **Study Schedule**

A study schedule summary follows for HP group arms:

- Visit 1: Screening, recruitment, randomization and periodontal consultation was completed. PVS impressions were taken for fabrication of both prescription trays and customized stents created for clinical measurements if patient accepts and were recruited as subjects.
- Visit 2, Week 0: Data collected for clinical measurements with custom stents for RAL, PD and R-rec (Baseline). Delivery of prescription tray and first supervised instructions and placement of the gel for the treatment groups. OHI.
- Visit 3, Week 4: 4 weeks after the delivery of the tray and the gel; data collection of periodontal parameters with stent, 2 quadrants of SRP, reinforcement of OHI. Inquire if subjects had any adverse events with the use of hydrogen peroxide gel
- Visit 4, Week 5: No more than 1-week elapsed time since visit 4; SRP of 2 remaining quadrants, reinforcement of OHI.

- Visit 5, Week 13: Periodontal re-evaluation 8 weeks after last quadrant of SRP; data collection of periodontal parameters with stent, SRP on residual sites with detectable calculus, termination of peroxide use in HP13. For subjects enrolled in HP26 , new impressions were made for new prescription tray.
- (Visit 6, Week 14 [HP26 only]): New prescription tray delivery
- Visit 6, Week 17: Periodontal maintenance, reinforcement of OHI.
- Visit 7, Week 26: Data collection of periodontal parameters with stent (final exam), periodontal maintenance, reinforcement of OHI.

A study schedule summary follows for SRP arm:

- Visit 1: Screening, recruitment, and randomization. Data collection of periodontal parameters by residents and verified by attending periodontists. PVS impressions will be taken for fabricating of customized stents for clinical measurements if patient accept and are recruited as subjects.
- Visit 2, Week 0: Clinical measurements with stents (Baseline).
- Visit 3, Week 4: SRP and OHI
- Visit 3, Week 5: Remaining quadrants of SRP, reinforcement of OHI
- Visit 4, Week 13: Periodontal re-evaluation 8 weeks after last quadrant of SRP; data collection of periodontal parameters with stent, SRP on residual sites with detectable calculus, reinforcement of OHI
- Visit 5, Week 17: Periodontal maintenance, reinforcement of OHI
- Visit 6, Week 26: Data collection of periodontal parameters with stent, periodontal maintenance, reinforcement of OHI.

[figure not shown]

Figure 1. CONSORT Flow Diagram

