## **Statistical Analysis**

The primary outcome variables are PD reduction, RAL gain, and reduction in BOP. PD data was computed to provide a mean score per mouth. Secondary efficacy variables were BOP, and MQH. BOP was computed to provide a mean score per mouth for each clinical assessment and were analyzed using repeated measures (ANOVA). Outcome variable data analysis consisted of between-treatment and within-treatment (longitudinal) comparisons of PD and CAL at all examination time points using parametric procedures. Between-treatment and within-treatment comparisons employed baseline data and analysis of covariance (ANCOVA) for follow-up data. All comparisons were performed using two-sided hypothesis tests, and employed a 0.05 level of significance.

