## CHAPTER THREE

### RESULTS

There were total 15 subjects who completed the 6-month trial. There were 10 males with an mean age of 55.6 years and 8 males with an mean age of 51.1 years. There was a total of 3 patients in SRP group, 3 patients in HP13 group, and 9 patients in HP26 group. The mean pocket depth (PD) shown in figure 1 at baseline for SRP group was  $3.88 \pm 0.06$  mm (std. error),  $4.11 \pm 0.06$  mm for HP13, and  $3.83 \pm 0.04$  mm for HP26. At the 4-week examination, PD for SRP group decreased to  $3.67 \pm 0.06$  mm,  $4.06 \pm 0.06$  mm with HP13, and  $3.55 \pm 0.04$  mm for HP26. At the re-evaluation examination, PD for SRP group was  $3.30 \pm 0.06$  mm,  $3.43 \pm 0.06$  mm for HP13, and  $3.14 \pm 0.04$  mm for HP26. The final examination, PD were  $3.43 \pm 0.06$  for SRP,  $3.40 \pm 0.06$  mm for HP 13, and  $3.23 \pm 0.04$  mm for HP26. Repeated measure ANOVA showed significant difference in pocket depth among all time points in all treatment groups. In SRP group, no significant difference between baseline and 4 weeks in pocket depth and relative attachment level.

[figure not shown]

Figure 2. Mean PD in each group, SRP, HP13, and HP26.

Figure 2 shows the mean relative recession over time. The mean relative recession at baseline was  $3.28 \pm 0.06$  mm for SRP,  $2.87 \pm 0.06$  mm for HP13, and  $3.21 \pm 0.03$  mm for HP13. At 4-weeks, it was  $3.35 \pm 0.06$  mm for SRP,  $3.23 \pm 0.05$  mm for HP13, and  $3.15 \pm 0.03$  mm for HP26. At re-evaluation it was  $3.33 \pm 0.06$  mm for SRP,  $3.27 \pm 0.05$  mm for HP13, and  $3.29 \pm 0.03$  mm for HP26.

[figure not shown]

Figure 3. Mean R-Rec in each group, SRP, HP13, and HP26.

Figure 3 shows the mean relative attachment level. The mean RAL at baseline was  $7.16 \pm 0.08$  mm for SRP,  $6.97 \pm 0.07$  mm for HP13, and  $7.04 \pm 0.04$  mm for HP26. At 4-weeks, the RAL was  $7.02 \pm 0.08$  mm for SRP,  $7.29 \pm 0.07$  mm for HP13, and  $6.69 \pm 0.05$  mm for HP26. At re-evaluation the RAL was  $6.63 \pm 0.08$  mm for SRP,  $6.15 \pm 0.07$  mm for HP13, and  $6.39 \pm 0.04$  mm for HP26. At the final exam RAL was  $6.79 \pm 0.08$  mm for SRP,  $6.71 \pm 0.07$  mm for HP13, and  $6.53 \pm 0.04$  mm for HP26.

[figure not shown]

Figure 4. Mean RAL in each group, SRP, HP13, and HP26.

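### Sites needing re-treatment are dropped from the final data on a PD and RAL criterion, so site selection can depend on primary outcomes, and no all-sites analysis is planned

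*Combined protocol and SAP*

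**What the plan says.** - **Trigger** (Follow Up Care): "If deterioration of periodontal conditions is noted (i.e. PD deepening and losing RAL >1.5mm with or without bleeding on probing". Re-treatment of such sites is then recommended to the patient.
- **Data rule** (Follow Up Care): "Any sites requiring re-treatment, either non-surgical or surgical intervention will be excluded in final study data".
- **Primary outcomes** (Statistical Analysis): "The primary outcome variables are PD reduction, RAL gain, and reduction in BOP".
- **Unit of analysis** (Statistical Analysis): "PD data was computed to provide a mean score per mouth". The section says the same for BOP and states no unit for RAL. The planned methods are ANCOVA using baseline data and repeated-measures ANOVA.
- **First primary objective** (Introduction): whether adjunctive HP gel "results in a greater clinical improvement than SRP alone over a six-month period".
- **Week 13, all arms** (Study Schedule): "SRP on residual sites with detectable calculus".

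No readable section plans an analysis that keeps the excluded sites, says how values after re-treatment are handled, or gives the number of excluded sites by arm. The CONSORT diagram is not shown and might hold counts.

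**The concern.** The rule acts after randomisation and on the quantities being compared. It is also one-sided: a site that loses 2 mm of attachment can leave the data, while a site that gains 2 mm stays. It covers sites that require re-treatment, so a site first flagged at week 26 can be dropped although nothing had yet been done to it and its measurement is valid. Blinding the examiner does not help, because the bias comes from which sites are averaged and not from how they are measured.

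The rule also cannot be applied reproducibly. It does not give the visit from which the RAL loss is counted. It does not say whether an excluded site leaves only the week-26 mean or the earlier means too. If only the week-26 value goes, baseline and final means come from different sets of sites.

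Within an arm, exclusion makes week-26 PD and RAL look better than if the deteriorated values were kept. Compared with as-measured values the direction is less certain, since a re-treated site may have recovered. Between arms, the bias depends on how exclusion rates differ.

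**Working it through.** The plan states no figure to reproduce here. The check is an illustration of size. It assumes that the reported means are those left after exclusion, and every exclusion rate is assumed.

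**Inputs.** Arm means come from Results. Because "All the measurement will be at 1 mm increments", a loss above 1.5 mm is taken as 2 mm. On completers, Results says: "There was a total of 3 patients in SRP group, 3 patients in HP13 group, and 9 patients in HP26 group". With at least 20 teeth per patient (Eligibility Criteria) and six sites per tooth, SRP has at least 3 × 20 × 6 = 360 sites and HP26 at least 9 × 20 × 6 = 1,080.

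**RAL gain g, baseline to final.** SRP 7.16 − 6.79 = 0.37 mm; HP13 6.97 − 6.71 = 0.26 mm; HP26 7.04 − 6.53 = 0.51 mm. HP26 minus SRP is 0.14 mm.

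**All-sites gain when a share d was excluded, under three readings of the rule:**

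- **A. Loss counted from baseline, site removed at both visits:** g − d(g + 2). Each 1% excluded adds 0.0237 (SRP), 0.0226 (HP13) or 0.0251 mm (HP26) to the arm's gain.
- **B. Loss counted from week 13, site removed at both visits.** The site is assumed to have made the arm-mean gain up to week 13: SRP 7.16 − 6.63 = 0.53, HP26 7.04 − 6.39 = 0.65. Net loss from baseline is then 2 − 0.53 = 1.47 and 2 − 0.65 = 1.35 mm. Each 1% adds 0.01 × (0.37 + 1.47) = 0.0184 and 0.01 × (0.51 + 1.35) = 0.0186 mm. HP13 is left out because its week-13 RAL of 6.15 does not match PD 3.43 + R-Rec 3.27 = 6.70.
- **C. Loss counted from baseline, only the week-26 value dropped, site's baseline RAL b assumed 5.5 to 9 mm:** g − d(b + 2 − final mean). Each 1% adds 0.0071 to 0.0421 (SRP) or 0.0097 to 0.0447 mm (HP26).

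**All-sites HP26 − SRP contrast in RAL gain (mm), against 0.14 from the reported means:**

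| Assumed exclusion | A | B | C |
|---|---|---|---|
| 5% in both arms | 0.13 | 0.14 | 0.13 |
| SRP 5%, HP26 1% | 0.23 | 0.21 | 0.17 to 0.31 |
| SRP 1%, HP26 5% | 0.04 | 0.07 | 0.10 to −0.04 |

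For example, A in the last row is (0.51 − 0.05 × 2.51) − (0.37 − 0.01 × 2.37) = 0.3845 − 0.3463 = 0.04. In SRP, 5% is 18 of 360 sites, so with three completers one or two patients could set the arm's rate.

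**PD.** Reduction is 3.88 − 3.43 = 0.45 (SRP) and 3.83 − 3.23 = 0.60 mm (HP26), a contrast of 0.15. Under A with an assumed deepening of 1 to 2 mm, the three rows give 0.14, 0.21 to 0.25, and 0.04 to 0.08 mm.

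**BOP.** Results prints HP13 twice for the final visit; the 28% is read as HP26. Reduction is 45 − 44 = 1 point (SRP) and 63.1 − 28 = 35.1 points (HP26), a contrast of 34.1. Baseline means are left unchanged, and excluded sites are assumed to bleed at the final rates for pockets initially 5 mm or deeper (88% SRP, 78% HP26). The three rows then give 33.8, 35.8 and 32.0 points. If every excluded site bleeds, they give 33.3, 36.2 and 31.1.

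**The case against.** **The effect is hypothetical.** This stands. No removed site is documented, and the unequal rates above have no source in the document. The trigger is demanding, and every arm's mean PD and RAL at week 13 and at the final visit were better than at baseline. That makes frequent loss from baseline less likely, though means cannot exclude it.

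**The 0.14 mm contrast is a weak yardstick.** This also stands. The document neither reports nor tests it. With the printed standard errors (0.08 and 0.04) and visits treated as independent, its standard error is √(2 × 0.08² + 2 × 0.04²) = 0.13 mm. Correlation within sites would lower that figure and clustering within patients would raise it. Under A, excluding 0.14/2.51 = 5.6% of HP26 sites (about 60 of 1,080) and none in SRP would account for the whole contrast. A reader might infer that a demonstrated benefit is at risk. The document does not support that, because no such benefit is established with 3 and 9 completers.

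**No stated conclusion depends on it.** Largely true. The efficacy statements in the Conclusion stop at 3 months, and the Discussion's efficacy claim is for BOP, which moves little. But the first primary objective runs to six months and needs the week-26 PD and RAL comparison.

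**Excluding re-treated sites can be a legitimate target.** It can, if the question is the effect without extra treatment. But dropping the sites that did badly does not answer that question; it averages the sites that did well enough not to need help.

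**The week-13 SRP is a separate matter.** A reader might infer that all sites scaled again at week 13 also leave the data. The natural reading is otherwise: that SRP is scheduled in every arm and prompted by calculus, whereas re-treatment in Follow Up Care follows from deterioration. This is a wording query only.

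**Conclusion.** The point holds and should be fixed. Followed as written, the rule allows sites to be removed after randomisation because of their PD and RAL results, and nothing in the readable plan offsets this. It is more than a missing detail, but it is not evidence that the reported results are wrong.

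If an excluded site leaves both visits, each 1% excluded with a 2 mm loss adds about 0.02 mm to an arm's mean RAL gain. If only its week-26 value is dropped, the range is 0.007 to 0.045 mm. Similar rates in the arms leave the contrast almost unchanged; a difference of four percentage points moves it by roughly 0.03 to 0.18 mm in the cases shown. These figures rest on assumed rates, a 2 mm loss and, under C, an assumed baseline RAL.

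A reader might infer that exclusion favoured the HP arms. The document does not support this: no count is given, and more exclusions in SRP would understate the HP benefit. Nor is the effect necessarily confined to week 26. That is the main exposure, but the earlier means change too if sites are removed at all visits.

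**What to change.** For analysis purposes, replace the exclusion sentence with:

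> The main week-26 analysis of PD, RAL and BOP keeps all sites measured at baseline in patients with a week-26 examination, with the same sites at every visit. A site first flagged at week 26 keeps its measured value. A site re-treated earlier for deterioration enters with its last value before re-treatment. Sensitivity analyses (i) use the as-measured week-26 value and (ii) exclude these sites at all visits. Sites with no week-26 value for other reasons, such as tooth loss, and patients without a week-26 examination are counted by arm. Flagged, re-treated and excluded sites and patients are reported by arm.

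In addition:

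- State the visit from which RAL loss is counted for this data rule.
- State the unit of analysis for RAL.
- Say in one sentence whether the scheduled week-13 SRP falls outside the rule.
- Label the re-analysis post hoc, because results are already reported. If no site was excluded, reporting that count is enough.

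Clinical re-treatment is unchanged.

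The cost is a few sentences and a rerun. Re-treated sites and their dates must be found in the patient records, since the document describes no site-level log. The schedule lists no stent measurement between weeks 13 and 26, so for a site re-treated in that interval the last recorded value may be the week-13 one; the report should say how often this occurs.

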## **Study Schedule**

A study schedule summary follows for HP group arms:

- Visit 1: Screening, recruitment, randomization and periodontal consultation was completed. PVS impressions were taken for fabrication of both prescription trays and customized stents created for clinical measurements if patient accepts and were recruited as subjects.
- Visit 2, Week 0: Data collected for clinical measurements with custom stents for RAL, PD and R-rec (Baseline). Delivery of prescription tray and first supervised instructions and placement of the gel for the treatment groups. OHI.
- Visit 3, Week 4: 4 weeks after the delivery of the tray and the gel; data collection of periodontal parameters with stent, 2 quadrants of SRP, reinforcement of OHI. Inquire if subjects had any adverse events with the use of hydrogen peroxide gel
- Visit 4, Week 5: No more than 1-week elapsed time since visit 4; SRP of 2 remaining quadrants, reinforcement of OHI.

- Visit 5, Week 13: Periodontal re-evaluation 8 weeks after last quadrant of SRP; data collection of periodontal parameters with stent, SRP on residual sites with detectable calculus, termination of peroxide use in HP13. For subjects enrolled in HP26 , new impressions were made for new prescription tray.
- (Visit 6, Week 14 [HP26 only]): New prescription tray delivery
- Visit 6, Week 17: Periodontal maintenance, reinforcement of OHI.
- Visit 7, Week 26: Data collection of periodontal parameters with stent (final exam), periodontal maintenance, reinforcement of OHI.

A study schedule summary follows for SRP arm:

- Visit 1: Screening, recruitment, and randomization. Data collection of periodontal parameters by residents and verified by attending periodontists. PVS impressions will be taken for fabricating of customized stents for clinical measurements if patient accept and are recruited as subjects.
- Visit 2, Week 0: Clinical measurements with stents (Baseline).
- Visit 3, Week 4: SRP and OHI
- Visit 3, Week 5: Remaining quadrants of SRP, reinforcement of OHI
- Visit 4, Week 13: Periodontal re-evaluation 8 weeks after last quadrant of SRP; data collection of periodontal parameters with stent, SRP on residual sites with detectable calculus, reinforcement of OHI
- Visit 5, Week 17: Periodontal maintenance, reinforcement of OHI
- Visit 6, Week 26: Data collection of periodontal parameters with stent, periodontal maintenance, reinforcement of OHI.

[figure not shown]

Figure 1. CONSORT Flow Diagram

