## ABSTRACT OF THE THESIS

Custom Application of Peroxide Gel as Adjunct to Scaling/Root planning in Treatment of Periodontitis

by

[name]

Master of Science, Graduate Program in Periodontics

Loma Linda University, September 2019

[name] [name], Chairperson

**Aim:** This study was aimed to evaluate and compare the clinical effects of scaling and root planning (SRP) combined with local delivery of 1.7% HP in customized trays to that of SRP alone.

**Materials and Methods:** Sixty patients with generalized moderate to chronic severe periodontitis will be assigned to three groups treated by SRP plus HP gel with a custom prescription tray application. The test groups will receive twice daily 1.7% HP gel in custom trays four weeks prior to SRP and will continue to application for up to 3- and 6-months post-SRP. Baseline data that is collected at the start of the study will be collected again at 4, 13, and 26 weeks post-SRP and analyzed for any changes and thus main outcome variables will include changes in pocket depth (PD), relative recession (R-Rec), relative attachment level (RAL), and changes in bleeding (BOP) using ANCOVA of main effects.

**Results:** Repeated measure ANOVA showed significant difference in pocket depth among all time points in all treatment groups. Mean BOP was significantly reduced in all groups between 4-week examination and re-evaluation with mean BOP scores at final

examination staying similar to levels at re-evaluation for HP13 and HP26 groups. Mean BOP scores at final examination group for SRP group was similar to baseline.

**Discussion:** The use of adjunctive HP in custom fabricated trays presents with no adverse effects. Significant improvement was evident in pocket depth and attachment level in both treatment groups between after 4 weeks of using the tray. No significant effect found in SRP group between baseline and 4 weeks. After SRP, significant difference was seen in all three groups between 4 weeks and 3 months.

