### **Treatment Phase**

The treatment phase began with non-surgical periodontal treatment. The two therapy test groups will have used their customized application HP gel for four weeks prior to the start of treatment. Non-surgical periodontal treatment consisted of 1-, or 2-visit SRP using ultrasonic and hand instrumentation with local anesthesia. Surfaces were to be deemed clean and debrided when subgingival deposits cannot be tactiley detected and the root surface feels smooth to the operator. Re-evaluation of SRP was done 8 weeks after the last session of SRP, at week 13. One therapy test group stopped using the HP

therapy at the re-evaluation visit (HP13). Whereas the other test therapy group received impressions for a new customized tray to continue application of HP therapy for an additional 13 weeks (HP26) to the termination of the study.

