### **Maintenance Phase**

All subjects were recalled 4 weeks after re-evaluation of SRP was done for periodontal maintenance and again 3 months later for their final maintenance. In the HP26 group, subjects continued to use twice-daily HP gel for 15 minutes until the termination of the study, at week 26. Measurements for all subjects, correspondingly, were taken at week 26. Patients enrolled in the study were maintained with 3-month maintenance intervals for the duration of the study (See section Follow Up Care).

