### **Custom HP Tray Application**

The principal investigator supervised first use of trays and HP gel and, if needed, adjustment were made to trays so that it seated completely and comfortably in the subject's mouth while maintaining an adequate seal. Each subject applied a thin ribbon of gel throughout tooth indentations to provide a dosage of ~0.75 gram in each tray using a mass scale. Treatment frequency will be fixed throughout the study duration: Start of Treatment (Visit 2, Week 0) to 8-weeks following SRP (Visit 5, Week 13): two treatments per day, 15 minutes each

Subjects in the treatment groups documented tooth brushing and the gel tray applications in calendar journals for the entire duration of the study. Subject compliance was estimated throughout the study by reviewing diaries and by massing gel tubes at each visit. Patients were instructed to bring in their treatment tubes to each visit.

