## **CHAPTER FIVE**

### **CONCLUSION**

In conclusion, the use of adjunctive HP in custom fabricated trays presents with no adverse effects. Significant improvement was evident in pocket depth and attachment level in both treatment groups between after 4 weeks of using the tray. No significant effect found in SRP group between baseline and 4 weeks. After SRP, significant difference was seen in all three groups between 4 weeks and 3 months.

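### The Abstract and Conclusion say the gel had no adverse effects, without limit, but the only documented enquiry is at week 4 of 13 or 26 weeks of use

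*Combined protocol and SAP*

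**What the plan says.** In Chapter Two, Study Schedule, the list for the gel arms has one adverse-event item, at Visit 3, Week 4: "Inquire if subjects had any adverse events with the use of hydrogen peroxide gel". The entries for weeks 5, 13, 14, 17 and 26 contain no such item, and neither does any visit in the SRP arm.

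Gel use runs well past week 4. HP13 stops at the week-13 re-evaluation (Treatment Phase). In HP26, "subjects continued to use twice-daily HP gel for 15 minutes until the termination of the study, at week 26" (Maintenance Phase).

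The Results text gives no adverse-event count and no number of patients asked, even for week 4. The Discussion paragraph of the Abstract nevertheless states: "The use of adjunctive HP in custom fabricated trays presents with no adverse effects". Chapter Five, Conclusion, repeats the sentence.

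**The concern.** A statement that a treatment had no adverse effects is only as broad as the search for them. Here the documented search is one question, four weeks into a regimen of 13 or 26 weeks.

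The secondary objective in Chapter One compares three with six months of gel, so a reader will take the safety sentence to cover the longer course. A clinician choosing that course would rely on it for weeks 13 to 26, where no enquiry is documented. The week-4 question also falls at the visit where SRP begins, so none is documented for gel use after SRP. The SRP arm is not asked at all, which leaves no background rate for comparison.

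**Working it through.** The plan states no adverse-event rate or count, so there is no figure to reproduce. The check compares documented enquiry with gel exposure.

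**Inputs**
- Gel starts at week 0 in both gel arms and ends at week 13 (HP13) or week 26 (HP26): Custom HP Tray Application, Treatment Phase, Maintenance Phase.
- The one enquiry is at week 4, taken to look back to week 0: Study Schedule.
- Completers: 3 in HP13 and 9 in HP26, so 12 gel users (Results). Planned: 20 per arm, so 40 gel users (end of Exclusion Criteria).

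**Share of gel weeks covered**
- HP13: 4/13 = 31%.
- HP26: 4/26 = 15%. If no gel was used between week 13 and delivery of the new tray at week 14, this becomes 4/25 = 16%.

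**Visits after week 0 during gel use that have a documented enquiry**
- HP13 (weeks 4, 5, 13): 1 of 3.
- HP26 (weeks 4, 5, 13, 14, 17, 26): 1 of 6.
- HP26 after week 13 (weeks 14, 17, 26): 0 of 3.

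**Pooled gel patient-weeks**

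| | Completers | Planned |
|---|---|---|
| Total | 3×13 + 9×26 = 273 | 20×13 + 20×26 = 780 |
| Covered by the week-4 enquiry | 12×4 = 48 (18%) | 40×4 = 160 (21%) |
| HP26, weeks 13 to 26, no documented enquiry | 9×13 = 117 (43%) | 20×13 = 260 (33%) |

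**What zero events would show**

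The exact one-sided 95% upper limit for zero events in n patients is 1 − 0.05^(1/n). The number asked is not stated in the text, so n is an assumption, ranging from the 12 gel completers to the 40 planned.
- n = 12: 1 − 0.05^(1/12) = 22%.
- n = 40: 1 − 0.05^(1/40) = 7%.
- For weeks 13 to 26, only the 9 HP26 completers are known to have been followed through. Had all 9 been asked and reported nothing, the limit would be 1 − 0.05^(1/9) = 28%.

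Even a complete enquiry with no events would therefore leave room for a fairly common reaction.

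**The case against.** The strongest reply is that the schedule is a summary and leaves out things that were done. Custom HP Tray Application says "Subject compliance was estimated throughout the study by reviewing diaries and by massing gel tubes at each visit", yet the schedule does not list this. Adverse events could have been asked about in the same way. Case report forms exist but their content is not shown, and the CONSORT diagram (Figure 1) is missing from the text available and might show withdrawals and their reasons. All of this stands: the documents do not show that nobody asked, and spontaneous reports are not ruled out.

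A second reply is that patients were observed in other ways. Full-mouth stent measurements were taken at weeks 13 and 26, Follow Up Care provides for monitoring of periodontal status, and the Discussion reads the recession data as evidence that the tray does no harm at the margin. Exclusion criterion 13 also names lasting tooth sensitivity and mucosal reactions to the gel, so the investigators had these in mind. This stands in part, because the stent data do bear on recession and attachment. But probing does not detect sensitivity, the diaries are described as recording brushing and tray use only, and criterion 13 gives no timing or method for finding the reactions it names.

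Nor are the tissue data uniformly reassuring. Between baseline and week 4, HP13 mean relative recession went from 2.87 to 3.23 mm and mean relative attachment level from 6.97 to 7.29 mm. With 3 completers in that arm, and HP26 attachment level moving the other way (7.04 to 6.69 mm), this is not evidence of harm. It does mean these measurements cannot carry an unlimited safety statement. The Results text also gives no week-26 recession values.

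Finally, safety is not a stated objective. That is true and limits the weight of the point. The claim still appears first in both the Abstract's Discussion and the Conclusion, so it needs support.

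**Conclusion.** The concern holds, as a minor point. The two safety sentences go beyond the documented enquiry, which covers about a third of the gel course in HP13, about a sixth in HP26, and about a fifth of all gel patient-weeks. Nothing is documented for weeks 13 to 26 or for gel use after SRP.

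These shares assume gel use from week 0 to weeks 13 and 26, and that the week-4 question covered the whole period since week 0. The Abstract instead describes use for up to three and six months after SRP; a longer course would make the covered share smaller. The upper limits of 22% and 7% depend on the assumed number asked. The conclusion itself rests only on the schedule and the two sentences. No efficacy result is affected.

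**What to change.** **Data in hand.** Check the case report forms and clinic notes for enquiries or spontaneous reports after week 4. If there are any, report them by arm with the number asked. If not, replace both sentences with a limited one, if it is true: *no adverse event was reported at the week-4 enquiry*, followed by the number of gel users asked and the exact upper limit for that number. State that no enquiry is documented after week 4 or in the SRP arm. The cost is two reworded sentences and one added number, and the safety statement becomes less favourable. Enquiries that were never made cannot be supplied afterwards.

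**Further patients, or reuse of the protocol.** Add one case report form line at every existing visit after week 0, asking about tooth sensitivity, mucosal reaction and any other event. Word it without reference to the gel so that the SRP arm can be asked as well. Have someone other than the outcome examiner ask it, because measurements are made "by the same examiner who was blinded to the treatment rendered to the subjects" and the answers could reveal the arm. No new visit is needed; the cost is slightly more data entry.
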